10 SAFETY ASSESSMENTS

The planned Schedule of Assessments is included in [Section 3](#).

10.1 Definitions

10.1.1 Adverse Event

An AE is any untoward medical occurrence experienced by a patient in a clinical investigation; it does not necessarily have a causal relationship with this study drug. An AE can therefore be any unfavorable and unintended sign, symptom, or disease temporally associated with the use of a medicinal product, whether or not considered related to the medicinal product.

Active or worsening of EPI is not considered an AE for the purposes of this study. Worsening of EPI disease should not be recorded as an AE but should be recorded in the appropriate EPI CRF.

Adverse events may also include post dose complications that occur as a result of protocol-mandated procedures (e.g., invasive procedures such as venipuncture, biopsy, etc.). Preexisting events that increase in severity or change in nature during, or as a consequence of, use of a medicinal product in a human clinical study will also be considered AEs. Any preexisting medical condition or diagnosis associated with a clinically significant laboratory abnormality should be documented on the CRF or eCRF. The Investigator should attempt to establish a diagnosis of the event based on signs, symptoms, and other clinical information. In such cases, the unifying diagnosis should be documented as the AE, rather than the individual signs and symptoms (e.g., runny nose, scratch throat, cough, and low grade fever should be recorded as an upper respiratory infection and not each of the individual symptoms).

An AE does NOT include the following:

- Medical or surgical procedures (e.g., surgery, endoscopy, tooth extraction, transfusion); the condition that necessitates the procedure is an AE
- Any preexisting disease or condition or laboratory abnormality present or detected before the start of administration of study medication that does not worsen
- Laboratory abnormalities without clinical manifestations, which do not require medical intervention, or that do not result in termination or delay of study medication
- Situations where an untoward medical occurrence has not occurred (e.g., hospitalization for elective surgery, social, or convenience admissions)
- Overdose of any study drug or concomitant medication without any signs or symptoms, unless the patient is hospitalized for observation
- Worsening and/or flares of EPI disease activity. This should be recorded in the appropriate EPI CRF. However, if disease worsening meets any of the criteria for an SAE, it must be recorded on the SAE form and reported to First Wave BioPharma or designee within 24 hours of becoming aware of the event.

10.1.2 Serious Adverse Event

An SAE is defined as any adverse experience occurring at any dose of study medication that occurs between the time the patient signs the informed consent form through the end-of-study that results in any of the following outcomes:

- Death
- Life-threatening situation (patient is at immediate risk of death)
- In-patient hospitalization or prolongation of existing hospitalization for a clinically relevant reason (note that this excludes “social” hospitalization for nonmedical causes such as lack of transportation to home)
- Persistent or significant disability/incapacity
- Congenital anomaly/birth defect in the offspring of a patient who received study drug
- Important medical events that may not result in death, be life-threatening, or require hospitalization may be considered serious when, based upon appropriate medical judgment, they may jeopardize the patient or patient may require medical or surgical intervention to prevent one of the outcomes listed in this definition. Examples may include, but are not limited to:
 - Intensive treatment in an emergency room or at home for allergic bronchospasm
 - Blood dyscrasias that do not result in hospitalization
 - Seizures that do not result in hospitalization

A hospitalization meeting the regulatory definition for “serious” is any in-patient hospital admission that includes a minimum of an overnight stay in a health care facility.

Worsening and/or flares of EPI disease activity should be recorded in the appropriate EPI CRF. However, if disease worsening meets any of the criteria for an SAE, then it must be recorded on the SAE form and reported to First Wave BioPharma or designee within 24 hours of becoming aware of the event.

10.1.3 “Serious” vs “Severe” Adverse Event

To avoid confusion or misunderstanding over the difference between the terms “serious” and “severe,” which are not synonymous, the following note of clarification is provided (excerpted from International Council for Harmonisation [ICH] E2A):

The term “severe” is often used to describe the intensity (severity) of a specific event (as in mild, moderate, or severe myocardial infarction); the event itself, however, may be of relatively minor medical significance (such as severe headache). This is not the same as “serious,” which is based on patient/event outcome or action criteria usually associated with events that pose a

threat to a patient's life or functioning. Seriousness (not severity) serves as a guide for defining regulatory reporting obligations.

10.1.4 SAE Definition Clarifications

- Death is an outcome of an AE, and not an AE in itself.
- All deaths during study through the end-of-study, regardless of cause or relationship, must be reported.
- "Occurring at any dose" does not imply that the patient is actively receiving study drug at the time of the event.
- "Life-threatening" means that the patient was at immediate risk of death from the event as it occurred. This does not include an event that might have led to death, had it occurred with greater severity.
- Complications that occur during hospitalizations are AEs. If an AE prolongs hospitalization, it is an SAE.
- "In-patient hospitalization" means the patient has been formally admitted to a hospital for medical reasons, for any length of time, excepting situations where an untoward medical occurrence has not occurred (e.g., hospitalization for elective surgery, social, or convenience admissions). Hospitalization may or may not be overnight. It does not include presentation and care within an emergency department (although an emergency department visit may define a medically important event, which is also considered an SAE).
- If any AE worsens during the study and eventually meets the criteria for an SAE the AE should be recorded as a new SAE.

10.2 Reporting Procedures for All Adverse Events

AEs will be recorded in the CRF for all patients from the time the patient signs the informed consent form through the end of the study or patient withdrawal.

The Investigator is responsible for ensuring that all AEs (as defined in [Section 10.1](#) and as further specified below) observed by the Investigator or reported by patients are collected and recorded in the patients' medical records, in the CRF, and as an SAE in the electronic data capture system. These AEs will include the following:

1. All SAEs (as defined in [Section 10.1.2](#)) that occur.
1. All nonserious AEs (as defined in [Section 10.1.1](#)) that occur.

The following AE attributes must be assigned by the Investigator:

- AE diagnosis or syndrome(s) (if known, signs or symptoms if not known);
- event description (with detail appropriate to the event);

- dates of onset and resolution; severity; assessment of relatedness to study drug; and
- action taken with study medication.

The Investigator may be asked to provide follow-up information, discharge summaries, and extracts from medical records or CRFs.

It will be left to the Investigator's clinical judgment to determine whether the relatedness of an AE, and of sufficient severity to require the patient's removal from treatment or from the study. A patient may also voluntarily withdraw from treatment because of what he or she perceives as an intolerable AE. If either of these situations arises, the patient should be strongly encouraged to complete the End-of-Therapy assessments and be under medical supervision until symptoms cease or the condition becomes stable.

10.3 Grading of Adverse Events

The Investigator will be asked to provide an assessment of the severity of the AE using the categories noted below. This assessment is subjective, and the Investigator should use medical judgment to compare the reported AE to similar events observed in clinical practice. It is important to recognize that severity is not equivalent to event seriousness.

Grade 1 (Mild): usually transient; requires no special treatment and does not generally interfere with the patient's daily activities.

Grade 2 (Moderate): produces a mild to moderate level of inconvenience to the patient and may interfere with daily activities. These events are usually ameliorated by simple therapeutic measures.

Grade 3 (Severe): significantly interrupts daily activity and requires systemic drug therapy or other medical treatment.

10.4 Relationship to Study Drug

For each reported AE, the Investigator must make an assessment of the relationship of the event to the study drug using the following scale:

Unrelated: The event is definitely not or unlikely associated with study drug administration and is judged because of causes other than the study drug.

Related: Events considered to be related are those that follow a reasonable temporal sequence from administration of the study drug, that are not easily explained by another cause such as known characteristics of the patient's clinical state or other treatment or confirmed by improvement on stopping or slowing administration of the study agent (de-challenge), if applicable.

10.5 Serious Adverse Event Reporting Procedures

Serious adverse events will be recorded from the time the patient signs the informed consent form through the end of study. AEs will be followed until the event resolves or stabilizes, or until the end of study for that patient.

If the AE is an SAE and is assessed as “related to study drug”, it must be followed until either the event is considered stable or resolved.

Any SAE assessed as “unrelated to study drug” will be followed as clinically indicated until its resolution or, if not resolving, until considered stable or until the final study visit for that patient whichever comes first.

All SAEs that occur must be reported within 24 hours of discovery or notification of the event. Initial SAE information and all amendments or additions must be recorded as an SAE in the electronic data capture system and sent to First Wave BioPharma or designee.

If a patient is permanently withdrawn from the study because of an SAE, then this information must be captured as an SAE in the initial or follow-up electronic data capture record as well as the End-of-Therapy CRF.

The Investigator should notify the appropriate IEC/IRB of SAEs occurring at the site and other SAE reports received from First Wave BioPharma, in accordance with local procedures and statutes.

First Wave BioPharma will ensure that applicable regulatory authorities receive all relevant information on an SAE, in accordance with regulatory requirements. Results of First Wave BioPharma’s investigation of other safety information shall be submitted, as required.

10.6 Pregnancy Reporting Procedures

Patients must be instructed to inform the Investigator immediately if they or their partners become pregnant after the patient has received their first dose of investigational product during the study. The following actions should be taken in the event of a confirmed pregnancy:

1. For female patients, study drug should be discontinued immediately.
2. The pregnancy should be reported to the Safety Group within 24 hours of notification using the applicable Pregnancy Report Form.
3. The Investigator should counsel the patient regarding the possible effects of previous study drug exposure on the fetus and the need to inform the study site of the outcome of the pregnancy.
4. The patient or the patient’s pregnant partner must be monitored until the immediate postnatal period or until termination of the pregnancy. The outcome should be reported to the Medical Monitor using the Pregnancy Outcome Form.

Pregnancy is not an AE in and of itself. However, any pregnancy complications or elective terminations of a pregnancy for medical reasons will be recorded as an AE or SAE. A spontaneous abortion is always considered an SAE and will be reported as described in the AE and SAE sections ([Section 10.2](#) and [Section 10.5](#)). Furthermore, any SAE occurring as an adverse pregnancy outcome poststudy must be reported to the Medical Monitor.

10.7 Hepatic Monitoring

The following guidelines are provided for the management of serum transaminase elevations in patients with new, clinically meaningful increases in liver function tests occurring during the study. All cases of new (i.e., since screening) elevations in ALT or AST ≥ 3 times ULN or any questions concerning the management of a patient with elevated serum transaminases should be discussed with the study Medical Monitor.

Patients who experience a new (i.e., since screening) elevation in ALT or AST level to $\geq 3 \times$ ULN OR total bilirubin $\geq 1.5 \times$ ULN will have hepatic monitoring (ALT, AST, Bilirubin) until one of the following occurs:

- Withdrawal from study if elevation in ALT or AST level to $\geq 3 \times$ ULN is associated with a rise in total serum bilirubin to $\geq 2 \times$ ULN (without laboratory findings of cholestasis [elevated serum alkaline phosphatase $\geq 2 \times$ ULN])
- Withdrawal from study if elevation in ALT or AST level to $\geq 5 \times$ ULN is associated with new or exacerbated gastrointestinal (GI) symptoms (i.e., nausea, vomiting, right upper quadrant pain, and/or jaundice) and other causes are not evident
- Withdrawal from the study if elevation in ALT or AST is $\geq 10 \times$ ULN regardless of serum bilirubin level

Causes of acute elevation of transaminases should be considered and ruled out (e.g., viral hepatitis, concomitant medications).

Patients discontinued from study drug administration should resume porcine PERT therapy according to physician prescription.

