3 SCHEDULE OF ASSESSMENTS

Table 1: Schedule of Assessments Part 1

	SCREENING		ADRULIPASE TREATMENT			END OF	
	Consent and Initial Evaluations	CFA on PERT	Dispense	Optimize	Optimize	CFA on Adrulipase	STUDY/EARLY TERMINATION
Visit Number	1 ^a	2 ^b	3	4 (T) ^c	5 (T) ^c	6 ^b	7
Study Week	-6	-2	1	2	3	4	5
Study Days	-42	-14	1	5	10	16	28
Visit Window (days)	+7	±7	±2	±2	±2	+5	±7
Pre-Visit Instructions	X	X		X	X		
Supervised confinement		X				X	
Clinical Assessments							
Obtain informed consent	X						
Demographics	X						
Complete history and physical	X						
Focused physical exam ^d		X				X	X
Confirm CF diagnosis (Inclusion Criteria 4)	X						
Height/weight, vital signs (sitting)	X	X				X	
Inclusion/exclusion criteria review	X	X	X				
Concomitant medications	X	X	X	X	X	X	X

CONFIDENTIAL

	SCREENING		ADRULIPASE TREATMENT			END OF	
	Consent and Initial Evaluations	CFA on PERT	Dispense	Optimize	Optimize	CFA on Adrulipase	STUDY/EARLY TERMINATION
Visit Number	1 ^a	2 ^b	3	4 (T) ^c	5 (T) ^c	6 ^b	7
Study Week	-6	-2	1	2	3	4	5
Study Days	-42	-14	1	5	10	16	28
Visit Window (days)	+7	±7	±2	±2	±2	+5	±7
Adverse events	X	X	X	X	X	X	X
Confirm scheduled date for next supervised confinement visit	X				X		
Study Treatment							
Instruct regarding study drug adrulipase (dose optimization, low, medium, high)			X			X	
Full study drug accountability at the end of confinement						X	
Return Adrulipase at the end of confinement						X	
Record fat and protein intake and study drug taken at all meals and snacks			X			X	
Efficacy Measures							
Malabsorption signs & symptoms		X	X	X	X	X	X
72-hour controlled diet record		X				X	

	SCREENING		ADRULIPASE TREATMENT			END OF	
	Consent and Initial Evaluations	CFA on PERT	Dispense	Optimize	Optimize	CFA on Adrulipase	STUDY/EARLY TERMINATION
Visit Number	1 ^a	2 ^b	3	4 (T) ^c	5 (T) ^c	6 ^b	7
Study Week	-6	-2	1	2	3	4	5
Study Days	-42	-14	1	5	10	16	28
Visit Window (days)	+7	±7	±2	±2	±2	+5	±7
Marker-to-marker stool collection and stool weight ^f		X				X	
Laboratory Tests							
Urinalysis	X					X	
Pregnancy test (serum for V1 screening and urine dipstick for other visits) ^g	X		X			X	X
Hematology, clinical chemistry, PT/INR, and aPTT ^h	X					X	
Fasting ⁱ lipids (patient to come in fasting status) and pre-albumin	X					X	
Serum samples for anti-adrulipase lipase antibodies and adrulipase concentrations		X				X	X
Fecal pancreatic elastase ^j	X						
Diagnostic Test							
Spirometry	X						

	SCREENING		ADRULIPASE TREATMENT			END OF	

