	Consent and Initial Evaluations	CFA on PERT	Dispense	Optimize	Optimize	CFA on Adrulipase	STUDY/EARLY TERMINATION
Visit Number	1 ^a	2 ^b	3	4 (T) ^c	5 (T) ^c	6 ^b	7
Study Week	-6	-2	1	2	3	4	5
Study Days	-42	-14	1	5	10	16	28
Visit Window (days)	+7	±7	±2	±2	±2	+5	±7
Switch back to Prescribed Porcine PERT							
Switch back to prescribed porcine PERT ^k						X	X

a Screening procedures can occur up to 14 days before the first day of supervised confinement (V2). As some lab assessments require fasting status, site may utilize a pre-screening telephone consent process to obtain agreement in advance for patients to adhere fasting for at least 8 hours. Patients will also be asked to bring a stool sample to V1

b Visit 2 and Visit 6 are the first and second scheduled confinement visits and can take up to 7 days. A 5-day window is permitted around the scheduled confinement for both V2 and V6 to accommodate for scheduling. Dosing must have occurred for at least 16 days prior to the start of the scheduled confinement.

c Visits 4 and 5 are telephone visits to assess any changes to AEs and concomitant medications in addition to confirming the visit date for the next scheduled supervised confinement.

d The Focused Physical Exam will evaluate gastrointestinal tract, heart, and lungs.

e At the end of V6 (after the last stool sample has been collected), Patients will begin treatment with their prestudy porcine PERT.

f The stool samples will be sent to the central laboratory and CFA, CNA, and stool weight will be measured.

g A serum pregnancy test must be conducted in females of reproductive potential at screening Visit 1. Pregnancy status will be re-evaluated via urine pregnancy test in these Patients at Visit 3, 6 and at the End-of-Study or Early Termination visit (Visit 7).

h On the basis of laboratory safety values, unscheduled hepatic monitoring testing may be performed in patients with new, clinically meaningful increases in liver function tests occurring during the study, in consultation with study designated Medical Monitor. These tests are to be done through the central labs.

i Fasting labs should be taken after patients have been in a fasting status for at least 8 hours at Visits 1 and 6.

j Fecal pancreatic elastase will be collected at Visit 1 and sent for analysis to the central laboratory.

k At the end of the supervised confinement (once the second blue dye marker sample has been collected), patients will return to their prestudy porcine PERT dose.

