8.3.4 Removal of Patients from the Study

A patient may be withdrawn from the study at any time for any of the following reasons:

- Lost to follow-up
- Voluntary withdrawal of consent by the patient, for any reason, at any time
- Major protocol deviations that could compromise the interpretation of the study results
- Occurrence of an immunoallergic reaction
- Occurrence of an adverse reaction (i.e., an SAE related to IMP) that justifies the discontinuation of the IMP
- Pregnancy

The date of withdrawal and the reason for withdrawal must be fully documented in the case report form (CRF) and a short narrative description should be added in the patient's medical records.

If at the time of withdrawal, the patient has received the investigational study product (partially or totally), study staff should encourage the patient to complete the Early Termination Visit (Visit 7) for follow-up safety investigations. These patients will be included in the mITT efficacy and safety analyses.

If the reason for discontinuation is due to an AE, then the Investigator will seek to obtain follow-up information and to document the event until its resolution or stabilization. In any case, the Investigator will take all necessary measures to ensure the patient's safety and ensure the patient is treated in accordance with local standard of care.

If a patient is lost to follow-up, then the Investigator should make every effort to obtain maximum information on the reasons for the nonattendance to the visit and on the patient's state of health. All attempts will be documented in the patient's medical records.

Pregnancy

Patients will be instructed that known or suspected pregnancy occurring during the study, in patients or female partners of male patients, should be confirmed and immediately reported to

the Investigator. Any patient who becomes pregnant during the study must be promptly withdrawn from the study. Upon discontinuation from the study, only those procedures that would not expose the patient to undue risk will be performed. The Investigator should also be notified of pregnancy occurring during the study but confirmed after completion of the study. If a patient is subsequently found to be pregnant after inclusion in the study, any pregnancy will be followed to term, and the status of mother and child will be reported to First Wave BioPharma after delivery.

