8.5. Clinical Laboratory Evaluation

All summaries except for the shift tables will be presented overall and by dose. Subjects are classified by maximum dose of adrulipase received during the study.

Values at Screening (Visit 1) and at 3 weeks post first dose, as described in Section 3, for laboratory parameters for hematology, clinical chemistry, and urinalysis will be summarized for the safety population using descriptive statistics.

Shift tables based on classification of values with respect to the reference range (low, normal, high) will be summarized for the safety population for critical clinical chemistry and hematology laboratory tests.

Post-baseline elevations in alanine aminotransferase (≥ 3 times the upper limit of normal [ULN]), aspartate aminotransferase (≥ 3 times ULN), total bilirubin (≥ 1.5 times ULN) will be summarized at Screening and at 3 Weeks Post First Dose. Hematology, clinical chemistry, hepatic monitoring, urinalysis, lipids, and pregnancy results will be presented in data listings for subjects in the safety population.

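### Protocol 10.7 ends hepatic monitoring only on withdrawal for worsening liver tests, and SAP 8.5 counts elevations at a single post-baseline time point

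*Protocol*

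**What the plan says.** Protocol 10.7 starts hepatic monitoring when a patient has a new ALT or AST of at least 3 × ULN or a total bilirubin of at least 1.5 × ULN. Such patients "will have hepatic monitoring (ALT, AST, Bilirubin) until one of the following occurs". The list then holds three items, each a withdrawal from the study:

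- ALT or AST at least 3 × ULN with bilirubin at least 2 × ULN and no cholestatic pattern;
- ALT or AST at least 5 × ULN with new or worse gastrointestinal symptoms and no other evident cause;
- ALT or AST at least 10 × ULN, whatever the bilirubin.

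No test frequency is given. Footnote h to both schedule tables says that "unscheduled hepatic monitoring testing may be performed in patients with new, clinically meaningful increases in liver function tests occurring during the study", again with no end.

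In both schedule tables the row "Hematology, clinical chemistry, PT/INR, and aPTT" is marked at Visits 1 and 6 only. Visit 7, which is also the early termination visit, has no liver tests (Protocol 9.2.4).

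On follow-up, Protocol 8.3.4 says that after discontinuation for an AE "the Investigator will seek to obtain follow-up information and to document the event until its resolution or stabilization". Protocol 10.5 follows AEs until they resolve or stabilise, or until the patient's study ends, and follows drug-related SAEs until stable or resolved. Protocol 10.1.1 takes some laboratory abnormalities out of the AE definition.

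SAP 8.5 says that post-baseline elevations of ALT, AST (each at least 3 × ULN) and total bilirubin (at least 1.5 × ULN) "will be summarized at Screening and at 3 Weeks Post First Dose". Hepatic monitoring results go into data listings.

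**The concern.** A rule that starts extra testing needs a stated end. The only ends printed in 10.7 are events in which the liver tests get worse. Followed literally, the duty to test stops when a patient meets a withdrawal criterion, and it never stops for a patient whose values return to normal. Two sites could apply the same sentence differently, and the amount of liver data collected after an elevation would depend on the site.

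On the analysis side, a summary fixed at Visit 6 shows the value that triggers monitoring and not what the monitoring then finds. At stake is whether the planned safety table reports each patient's worst liver value, in a study whose Part 2 dose has not been used in prior studies (Protocol 6.7).

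**Working it through.** No sample size, power or event rate is involved. The check compares sections and makes simple counts.

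**1. End conditions in Protocol 10.7.** Three are listed. Withdrawal for worsening: 3 of 3. Recovery, return to baseline, stabilisation or end of study: 0 of 3. Nothing elsewhere in the documents says when hepatic monitoring ends.

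**2. Do the AE rules fill the gap?** Take the patients in two groups.

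- *Drug stopped because of the liver finding.* The 10.1.1 exclusion concerns abnormalities that are silent, need no intervention or do not cause study medication to be stopped or delayed. On its natural reading, a rise that makes the patient stop drug falls outside it and is an AE. Sections 8.3.4 and 10.5 then apply. The second withdrawal criterion also requires symptoms by definition. This group is largely covered, although neither section names ALT, AST or bilirubin.
- *Silent rise first found at Visit 6.* Adrulipase is returned on the last day of that confinement (Protocol 9.2.3), so dosing ends by schedule and not because of the result. The rise may then fail to qualify as an AE, and the AE follow-up rules need not reach it. Only 10.7 would, and 10.7 has the defect in step 1.

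**3. How likely is Visit 6 to be the trigger?** Scheduled chemistry draws after the first dose: 1 (Visit 6). Absent an unscheduled draw, every trigger arises there. From nominal Visit 6 admission to Visit 7 is 28 − 16 = 12 days in Part 1 and 21 − 10 = 11 days in Part 2. The schedule has no chemistry at Visit 7.

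**4. Time points counted in SAP 8.5.** Two are named: Screening and 3 weeks. SAP 8.6.1 equates 3 weeks with Visit 6. Screening precedes the first dose, so a value there cannot be a post-baseline elevation. Post-baseline time points counted: 2 − 1 = 1. Monitoring that starts from the Visit 6 result yields values after that point, so none of them enters the count. The 3-week label also does not describe Part 2, where Visit 6 is Day 10 + 3.

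**5. What the count misses.**

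- A patient below 3 × ULN for ALT at Visit 6, whose bilirubin triggers monitoring and whose ALT then passes 3 × ULN, is not counted for ALT. With about 12 patients, that one patient is 1/12 = 8.3%.
- Assumed example: ALT is 3.5 × ULN at Visit 6 and 11 × ULN on an unscheduled test. The patient is counted once at the 3 × ULN threshold either way. The peak is lost from the summary because the table has one threshold and one visit.

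**The case against.** The strongest reply is that the practical gap is small, and much of that reply stands. New transaminase elevations at or above 3 × ULN go to the Medical Monitor under 10.7, the AE rules cover most patients who stop drug, and an investigator is free to keep testing. Open-ended monitoring of a recovering patient errs towards more data. In a descriptive pilot of about 12, a reader can find a late peak in the listings. What remains is the printed list, the silent rise at Visit 6, and the summary count.

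Four stronger readings are tempting, and the documents do not support them:

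- *A reader might infer that 10.7 conflicts with 8.3.4.* One is a monitoring rule and the other an AE follow-up duty. Both can be obeyed, and 10.7 forbids no test. They need to be joined up, but they do not contradict each other.
- *A reader might infer that the trial could not say how many patients met the hepatic withdrawal criteria.* SAP 8.5 lists the hepatic monitoring results, SAP 6.1 counts withdrawals by reason, and SAP 8.4 tabulates TEAEs leading to treatment or study discontinuation. The number can be read from these outputs; it simply has no table of its own.
- *A reader might cite the liver SAE in Protocol 6.6.2, which lasted about two weeks, as proof that follow-up is too short.* Its enzymes were between 2 and 3 × ULN, below the 10.7 transaminase trigger of at least 3 × ULN. Its duration says nothing about when 10.7 monitoring should end.
- *A reader might see a contradiction between optional testing in footnote h and required testing in 10.7.* Footnote h covers any new, clinically meaningful increase, while 10.7 covers those crossing stated thresholds. Optional for the wider group and required for the subset is coherent, though a cross-reference would help.

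**Conclusion.** The point holds as a drafting defect in the protocol and a gap in one SAP summary. In 10.7, 0 of 3 printed end conditions describe recovery or stabilisation. In SAP 8.5, 1 of 2 time points is post-baseline, and later or unscheduled peaks reach the listings only.

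This rests on two readings. One is that the 10.1.1 exclusion can apply to a silent rise found as dosing ends on schedule. The other is that the 10.7 list was meant as withdrawal criteria and was attached to a sentence about monitoring. The second is the likely explanation, but the documents do not settle it.

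The consequence is modest. Most patients who stop drug for a liver event are covered elsewhere, and no data already collected are lost.

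**What to change.** **Protocol.** The sponsor should separate the end of hepatic monitoring from the withdrawal criteria in 10.7, and should set the clinical end point itself; none is proposed here. The revised text should be reconciled with footnote h, 8.3.4, 10.1.1 and 10.5, so that it is clear which rule governs a silent rise first seen at Visit 6.

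**SAP 8.5.** Count patients by their worst post-baseline ALT, AST and total bilirubin at any time, including unscheduled and post-treatment tests. Because a single threshold hides how high a value went, show the worst multiple of ULN as well; bands at the multiples that 10.7 already uses are an option. Keep the Screening column but relabel it as the baseline reference. It is useful because exclusion 6 lets the investigator enrol a patient with ALT or AST at or above 3 × ULN. Name the treatment time point as Visit 6, so that the label fits both parts.

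**Cost.** One protocol paragraph with its cross-references, and one SAP table. The table change uses data already planned for collection.
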